7.1.2. Adverse Events Caused by Cisplatin

Below is an excerpt from the package insert.

Summary

The incidence of adverse reactions and laboratory abnormalities in the 104 patients in Japanese clinical studies of patients with hepatocellular carcinoma was 99.0%. The most common adverse reactions included anorexia (79.8%), nausea/vomiting (76.0%), fever (63.5%), malaise (26.9%), leukopenia (78.8%), neutropenia (77.2%), thrombocytopenia (76.9%), elevated AST (GOT) (56.7%), hypochromia (51.0%), ALT (GPT) (45.2%), increased serum bilirubin (36.5%), decreased serum albumin (31.7%), decreased serum total protein (29.8%), increased LDH (27.9%), increased BUN (25.0%), and increased blood creatinine (21.2%). (At time of approval)

Clinically significant adverse reactions

- 1) Acute kidney injury (frequency unknown): Serious kidney injury such as acute kidney injury may occur. Monitor patients carefully, discontinue cisplatin, and take appropriate therapeutic measures if any abnormalities in BUN, serum creatinine, or creatinine clearance are observed. Hematuria, proteinuria, oliguria, and anuria may also occur.
- 2) Myelosuppression such as pancytopenia (frequency unknown): Pancytopenia, anemia, leukopenia, neutropenia, and thrombocytopenia may occur. Monitor patients carefully (e.g., by frequent hematology tests), reduce the dose of cisplatin, interrupt treatment or discontinue cisplatin, and take appropriate therapeutic measures if any abnormalities are observed.
- 3) Thrombocytopenia (frequency unknown): Sudden thrombocytopenia may occur 1-4 days after using cisplatin. Monitor patients carefully (e.g., by frequent hematology tests) after starting cisplatin and take appropriate therapeutic measures if any abnormalities are observed.
- 4) Fulminant hepatitis (frequency unknown), liver dysfunction (< 1%), and jaundice (frequency unknown): Serious liver dysfunction, fulminant hepatitis, and jaundice accompanied by elevated AST (GOT), ALT (GPT), Al-P, LDH, γ -GTP, or serum bilirubin may occur. Monitor patients carefully, reduce the dose of cisplatin, interrupt treatment or discontinue cisplatin, and take appropriate therapeutic measures if any abnormalities are observed. Abnormalities in serum albumin, serum total protein, and ICG may also occur. Repeated dosing with cisplatin may also cause cholestasis.
- 5) Myocardial infarction (< 1%), angina pectoris (frequency unknown), heart failure (frequency unknown), and arrhythmia (frequency unknown): Myocardial infarction, angina pectoris (including atypical angina), congestive heart failure, and arrhythmias (e.g., ventricular fibrillation, cardiac arrest, atrial fibrillation, and bradycardia) may occur.

Monitor patients carefully, discontinue cisplatin, and take appropriate therapeutic measures if chest pain, syncope, shortness of breath, palpitations, or abnormal ECG findings are observed.

6) Pulmonary tuberculosis (< 1%): Serious infectious diseases such as pulmonary tuberculosis may occur. Monitor patients carefully and discontinue cisplatin if any abnormalities are observed.

7) Hearing impairment (3.8%): Loss of high frequency hearing, hearing difficulty, and tinnitus may occur. The frequency of hearing impairment is known to increase as the dose of infusional cisplatin is increased, and is particularly high at a daily dose of 80 mg/m² or higher or a total dose of 300 mg/m². Thus, patients receiving these doses should be monitored carefully.

8) Shock and anaphylactoid symptoms (frequency unknown): Shock and anaphylactoid symptoms may occur. Monitor patients carefully, discontinue cisplatin, and take appropriate therapeutic measures if symptoms such as facial edema, bronchospasm, cyanosis, dyspnea, chest pain, or hypotension appear.

9) Papillary edema, retrobulbar neuritis, and cortical blindness (frequency unknown for all): Visual impairment such as papillary edema, retrobulbar neuritis, and cortical blindness may occur. Discontinue cisplatin if any abnormalities are observed.

10) Cerebral infarction (frequency unknown): Cerebral infarction may occur. Discontinue cisplatin if any abnormalities are observed.

11) Hemolytic uremic syndrome (frequency unknown): Hemolytic uremic syndrome characterized by thrombocytopenia, hemolytic anemia, and renal failure may occur. Monitor patients carefully by regular hematology tests (e.g., platelet and red blood cell counts) and renal function tests, discontinue cisplatin, and take appropriate therapeutic measures if any abnormalities are observed.

12) Hemolytic anemia (frequency unknown): Coombs-positive hemolytic anemia may occur. Discontinue cisplatin if any abnormalities are observed.

13) Interstitial lung disease (frequency unknown): Interstitial pneumonia accompanied by symptoms such as fever, coughing, dyspnea, and abnormalities on chest X-ray may occur. Monitor patients carefully, discontinue cisplatin, and take appropriate therapeutic measures (e.g., treatment with corticosteroids) if any abnormalities are observed.

14) Syndrome of inappropriate antidiuretic hormone secretion (frequency unknown): Syndrome of inappropriate antidiuretic hormone secretion (SIADH) characterized by hyponatremia, hypoosmolality, increased urinary sodium secretion, hypersthenuria, convulsions, and impaired consciousness may occur. If such symptoms appear, discontinue cisplatin, and take appropriate therapeutic measures (e.g., limiting fluid intake).

15) Gastrointestinal hemorrhage, gastrointestinal ulcer, and gastrointestinal perforation (frequency unknown for all): Gastrointestinal hemorrhage, gastrointestinal ulcer, and gastrointestinal perforation may occur. Monitor patients carefully, reduce the dose of cisplatin, interrupt treatment or discontinue cisplatin, and take appropriate therapeutic measures if any abnormalities are observed.

16) Acute pancreatitis (frequency unknown): Acute pancreatitis may occur. Monitor patients carefully and discontinue cisplatin if any abnormalities such as increased serum amylase or serum lipase are observed.

17) Hyperglycemia (frequency unknown) and worsening of diabetes (frequency unknown): Hyperglycemia and worsening of diabetes may occur. Complications such as coma and ketoacidosis have also been reported with infusional cisplatin. Monitor patients carefully by blood glucose and urine glucose tests, discontinue cisplatin, and take appropriate therapeutic measures if any abnormality is observed.

18) Rhabdomyolysis (frequency unknown): Rhabdomyolysis may occur. Discontinue cisplatin and take appropriate therapeutic measures if an increase in CK (CPK) or blood/urine myoglobin is observed.

7.1.3. Adverse events caused by fluorouracil

Below is an excerpt from the package insert.

Summary

The most common adverse reactions reported in 1936 patients at the time of approval and in adverse reaction studies up to February 1970 were anorexia (295 cases, 15.2%), diarrhea/loose stools (239 cases, 12.3%), general malaise (172 cases, 8.9%), nausea/vomiting (159 cases, 8.2%), leukopenia (153 cases, 7.9%), stomatitis (129 cases, 6.7%), hyperpigmentation (92 cases, 4.8%), and hair loss (74 cases, 3.8%).

Clinically significant adverse reactions

(1) Severe diarrhea may occur and may cause dehydration symptoms. Monitor patients carefully, discontinue fluorouracil, and take appropriate therapeutic measures (e.g., fluid replacement) if such symptoms appear.

(2) Serious enterocolitis (e.g., hemorrhagic enterocolitis, ischemic enterocolitis, and necrotizing enterocolitis) may occur. Monitor patients carefully, discontinue fluorouracil, and take appropriate therapeutic measures if symptoms such as severe abdominal pain and diarrhea appear.

(3) Myelosuppression (e.g., pancytopenia, leukopenia, neutropenia, anemia, and thrombocytopenia) may occur. Monitor patients carefully and take appropriate therapeutic measures (e.g., dose reduction or interruption) if any abnormalities are observed.

(4) Shock and anaphylactoid symptoms may occur. Monitor patients carefully,

immediately discontinue fluorouracil, and take appropriate therapeutic measures if symptoms such as rash, dyspnea, and hypotension are observed.

(5) Leukoencephalopathy (early symptoms: gait abnormality, numbness in the distal extremities, impaired tongue movement, etc.) or neuropsychiatric symptoms such as extrapyramidal symptoms, speech impairment, ataxia, nystagmus, impaired consciousness, convulsions, facial paralysis, disorientation, numbness in the distal extremities, delirium, memory loss, loss of motivation, and urinary incontinence may occur. Monitor patients carefully and discontinue fluorouracil if such symptoms appear.

(6) Congestive heart failure, myocardial infarction, and variant angina may occur. Monitor patients carefully and take appropriate therapeutic measures (e.g., dose reduction or interruption) if any abnormalities are observed.

(7) Serious renal impairment such as acute kidney injury may occur. Monitor patients carefully, discontinue fluorouracil, and take appropriate therapeutic measures if any abnormalities are observed. Be particularly cautious during coadministration of fluorouracil with antitumor agents known to cause renal impairment (e.g., cisplatin and methotrexate).

(8) Interstitial pneumonia may occur. Discontinue fluorouracil, perform tests such as a chest X-ray, and take appropriate therapeutic measures (e.g., treatment with corticosteroids) if respiratory symptoms such as fever, cough, and dyspnea appear.

(9) Liver dysfunction and jaundice associated with elevated AST (GOT), ALT (GPT), Al-P, and γ -GTP may occur, and some cases may result in hepatic failure. Monitor patients carefully, discontinue fluorouracil, and take appropriate therapeutic measures if any abnormalities are observed.

(10) Gastrointestinal ulcers and serious stomatitis may occur. Monitor patients carefully, and discontinue fluorouracil and take appropriate therapeutic measures if any abnormalities are observed.

(11) Acute pancreatitis may occur. Monitor patients carefully, discontinue fluorouracil, and take appropriate therapeutic measures if abdominal pain or increased serum amylase is observed.

(12) Hyperammonemia with impaired consciousness may occur. Monitor patients carefully, and discontinue fluorouracil and take appropriate therapeutic measures if any abnormalities are observed.

(13) Hepatic arterial infusion of fluorouracil can cause hepatobiliary impairment (e.g., cholecystitis, bile duct necrosis, and hepatic parenchymal impairment). Check the distribution of drugs carefully by imaging with contrast. Discontinue fluorouracil and take appropriate therapeutic measures if any abnormalities are observed.

(14) Hand and foot syndrome (e.g., palmar/plantar erythema, painful redness and swelling, and hyperesthesia) may occur. Monitor patients carefully and take appropriate therapeutic measures (e.g., dose reduction or interruption) if any abnormalities are observed.

(15) Olfactory impairment may occur (most often with long-term use), and can lead to anosmia. Monitor patients carefully and take appropriate therapeutic measures (e.g., discontinuation of fluorouracil) if any abnormalities are observed.

(16) Serious hepatic impairment (e.g., fulminant hepatitis), cirrhosis of the liver, ventricular tachycardia, nephrotic syndrome, Stevens-Johnson syndrome, toxic epidermal necrolysis (Lyell syndrome), and hemolytic anemia have been reported with similar drugs. Monitor patients carefully, discontinue fluorouracil, and take appropriate therapeutic measures if any abnormalities are observed.

7.2. Adverse Events Caused by Catheters and Reservoirs

Events such as bleeding associated with arterial puncture, hematoma, intimal injury, neuropathy, aneurysm, arteriovenous fistula, infection, pain (all rare), blood vessel perforation by the catheter/guidewire (rare), spasms and obstruction (rare), infection and pain (rare), nausea/vomiting (20%), vagal response (rare), shock caused by iodine contrast medium (very rare), and foreign matter left in blood vessels after equipment breakage (very rare) are anticipated to occur during catheterization before the start of the study. These events may also occur later. Events such as hemorrhage, hematoma, intimal injury, neuropathy, infection, and pain are also anticipated with reservoir placement.

7.3. Adverse Events Expected with Combination Chemotherapy

Sorafenib may exacerbate hemorrhage, hematoma, and intimal injury associated with reservoir placement. Patients will be monitored carefully for these.

7.4. Evaluation of Adverse Events/Adverse Reactions

Site investigators will look out for adverse events throughout the entire study period. Therefore, patients should be monitored carefully during the study and even after the end of the study. All adverse events (observed events, unsolicited events, and events described in medical interviews) must be described in detail on case report forms. The following items must be recorded.

- 1) Date of occurrence
- 2) Grade (Japanese translation of CTCAE v4.0)
- 3) Causal relationship of adverse event with each study drug (**causality definitions from Table 10**)

- 4) Assessment of the adverse event as serious* or non-serious
- 5) Outcome of the adverse event (resolved/not resolved)

Site investigators will determine the seriousness of each event that occurs. If the event is judged as serious*, they will submit necessary institutional reports in accordance with institutional procedures. In the event of a serious adverse reaction, site investigators will make an unsolicited report of necessary details to the manufacturer.

Table 10 Causality definitions

Category	Definition
No relationship	The event has no causal relationship with the protocol treatment, and can be clearly explained by other factors such as progression of the primary disease, comorbid disease, or other drugs or treatments
Possible relationship	The event could possibly have a causal relationship with the protocol treatment, but could also be explained by other factors such as progression of the primary disease, a concomitant disease, or other drugs or treatments
Relationship	The event has a clear causal relationship with the protocol treatment and cannot be explained by other factors such as progression of the primary disease, comorbid disease, or other drugs or treatments

*: Events that meet the following criteria are defined as serious.

- 1) Death
- 2) Disability (dysfunction severe enough to interfere with ADL)
- 3) Life-threatening
- 4) Risk of disability
- 5) Hospitalization or prolongation of existing hospitalization for treatment is indicated
- 6) Equivalently serious to 1) through 5)
- 7) Congenital anomaly or birth defect

Site investigators will properly diagnose and treat events to minimize patient risks. They will also perform appropriate diagnostic tests to collect evidence that clarifies the causality of serious adverse events.

8. PARAMETERS ASSESSED, CLINICAL TESTS, AND ASSESSMENT

SCHEDULE

8.1. Parameters Assessed Before Enrollment

Data on the following parameters will be collected within 4 weeks before enrollment for pre-enrollment evaluation.

- 1) Patient characteristics: Sex, height, pathological diagnosis, treatment history, disease stage (using the General Rules for the Clinical and Pathological Study of Primary Liver Cancer, see Section 21.3), ECOG-PS (see Section 21.2), allergies, and concomitant diseases
- 2) Signs and symptoms and blood pressure
- 3) Body weight
- 4) Chest X-ray
- 5) Electrocardiogram
- 6) Target lesion measurements (dynamic CT is preferred, but dynamic MRI is also acceptable)
- 7) Hematology parameters: Hemoglobin, white blood cell count, neutrophil count, red blood cell count, platelet count
- 8) Blood biochemistry: AST, ALT, total bilirubin, direct bilirubin, ALP, γ -GTP, albumin, creatinine, Na, K, Cl, amylase, lipase, blood glucose
- 9) Coagulation: PT (INR)
- 10) Tumor markers: AFP, AFP-L3 fraction, PIVKA-II
- 11) Hepatitis virus: HBs antigen/HBs antibody/Hbc antibody,*¹ HCV antibody*²

*1 If the patient tests positive for Hbs antibody and/or Hbc antibody, HBV DNA will be analyzed following the methods in the “Guidelines for Management of Hepatitis B Virus Caused by Immunosuppressive Therapy and Chemotherapy” [28] (see **21.5 Guidelines for Management of Hepatitis B Virus Caused by Immunosuppressive Therapy and Chemotherapy**).[[not a link]] Patients who test positive for HBV DNA will be provided appropriate treatment.

*2 Patients who test positive will be tested for HCV RNA and serotype.

8.2. Tests and Evaluations during the Study Period

8.2.1. Parameters evaluated during the first cycle

Data on the following parameters will be collected each week during the first cycle.

- 1) Signs and symptoms* and blood pressure
- 2) Hematology parameters: Hemoglobin, white blood cell count, neutrophil count, red blood cell count, platelet count

3) Blood biochemistry: AST, ALT, total bilirubin, direct bilirubin, ALP, γ -GTP, albumin, creatinine, Na, K, Cl, amylase, lipase, blood glucose

*: Signs and symptoms will be recorded using terms from the Japanese translation of CTCAE v4.0.

4) Coagulation: PT (INR)

5) Adherence to study treatment

8.2.2. Parameters evaluated from the second cycle onward

Data on the following parameters will be collected right before each cycle from the second cycle onward.

1) Signs and symptoms* and blood pressure

2) Body weight

3) Target lesion measurements (dynamic CT is preferred, but dynamic MRI is also acceptable)

4) Hematology parameters: Hemoglobin, white blood cell count, neutrophil count, red blood cell count, platelet count

5) Blood biochemistry: AST, ALT, total bilirubin, direct bilirubin, ALP, γ -GTP, albumin, creatinine, Na, K, Cl, amylase, lipase, blood glucose

*: Signs and symptoms will be recorded using terms from the Japanese translation of CTCAE v4.0.

6) Coagulation: PT (INR)

7) Tumor markers: AFP, AFP-L3 fraction, PIVKA-II

8) Adherence to study treatment

8.3. Tests and Evaluations after Discontinuation of the Protocol Treatment

As much of the following data as possible will be collected in order to evaluate efficacy and safety (within 1 month of the date of discontinuation of the protocol treatment).

1) Signs and symptoms and blood pressure

2) Body weight

3) Target lesion measurements (dynamic CT is preferred, but dynamic MRI is also acceptable)

4) Hematology parameters: Hemoglobin, white blood cell count, neutrophil count, red blood cell count, platelet count

5) Blood biochemistry: AST, ALT, total bilirubin, direct bilirubin, ALP, γ -GTP, albumin, creatinine, Na, K, Cl, amylase, lipase, blood glucose

6) Coagulation profile: PT (INR)

7) Tumor markers: AFP, AFP-L3 fraction, PIVKA-II

8) Adherence to sorafenib

8.4. Follow-up after Discontinuation of the Protocol Treatment

The following items will be monitored to the greatest extent possible from the time protocol treatment is discontinued until the end of the entire study. Tests will be performed at the investigator's discretion depending on the patient's condition and will not be defined as part of this study.

- 1) Survival: Date survival was last confirmed or date of death; if dead, cause of death
- 2) Disease progression*: Whether the disease has progressed, date of last follow-up regarding progression or date progression was confirmed, site of progression
- 3) Post-trial treatment: Whether patient is receiving post-trial treatment, treatments received, start date

*Patients who enter the follow-up stage before progression is confirmed will be followed until progression. Reporting is not necessary after progression.

8.5. Imaging

Lesions will be imaged by dynamic CT or dynamic MRI 4 weeks (\pm 1 week) after the start of treatment and every 8 weeks thereafter until progression is confirmed.

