6. TREATMENT PLANS AND CRITERIA FOR ADJUSTING TREATMENT

6.1. Protocol Treatments

6.1.1. Low-dose FP and sorafenib group (combination therapy group) (Table 1)

This study will use the following doses demonstrated as safe in a phase I/II study of sorafenib and low-dose cisplatin/fluorouracil hepatic arterial infusion chemotherapy for advanced hepatocellular carcinoma. Cisplatin will be administered at a dose of 20 mg/m² on day 1 (within 30 days), and fluorouracil will be administered at a dose of 330 mg/m²/day by hepatic infusion using a reservoir for 5 days from day 1 through day 5 (continuous infusion over 24 h), followed by 2 days off. This sequence will be repeated for 2 weeks, followed by 2 weeks off. Sorafenib will be administered continuously at a dose of 400 mg twice daily for 28 days from day 1 to day 28. This 4-week period constitutes one cycle.

The first cycle of treatment will be started within 28 days of randomization. Treatment with sorafenib before hepatic arterial infusion chemotherapy will be allowed. However, patients must be off sorafenib for 2 days before and 7 days after reservoir placement. The next cycle of treatment will be started within 14 days. Sorafenib will be continued until the start of the next cycle. This combination therapy will be continued until discontinuation of the protocol treatment.

If an adverse event is observed, treatment will be interrupted or the dose will be reduced as appropriate in accordance with **6.3.2. Criteria for adjusting the sorafenib dose (dose interruption and reduction)** and **Section 6.3.3. Criteria for Hepatic Arterial Infusion Chemotherapy (Low-dose FP) Dose Adjustment (Dose Interruption and Reduction)**. After the protocol treatment is discontinued, appropriate treatment as described in **Section 6.5 Post-trial Treatment** will be instituted.

The arterial catheter should be placed in a manner that allows for proper drug distribution throughout the liver, and the flow should always be checked by contrast CT through the port or by DSA before starting treatment.

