6.3. Criteria for Treatment Adjustment

6.3.1. Criteria for starting the next cycle (for both groups)

The next cycle will be started if the investigator confirms the following criteria are met within 1 week before the scheduled start date. If any of these criteria are not met, the interval to the next cycle will be extended and the next cycle will be started as soon as the criteria are met. The next cycle cannot be started if the patient is off sorafenib. The start date of the next cycle can be extended for up to 8 weeks from the end of the previous cycle. If the criteria for starting the next cycle are still not met after that period, the protocol treatment will be discontinued.

- 1) Neutrophil count $\geq 1,000/\mu\text{L}$
- 2) Platelet count $\geq 50,000/\mu\text{L}$
- 3) Total bilirubin ≤ 2 mg/dL
- 4) ALT and AST ≤ 6 times the institutional upper limit of normal
- 5) Serum creatinine ≤ 1.5 times the institutional upper limit of normal
- 6) Amylase ≤ 2 times the institutional upper limit of normal

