8.6. Study Schedule

Observations and tests for evaluating safety and efficacy will be performed following the schedule below (Table 11).

Table 11 Schedule of observations and tests

		Before treatment	During protocol treatment				At termination	After discontinuation of the protocol treatment
Cycle	1				Right before the start of each cycle			
Week	1		2	3	4			
Patient characteristics* ¹		○						
Signs and symptoms, and blood pressure		○	○	○	○	○	○	
Body weight		○	○	○	○	○	○	
Chest X-ray		○						
Electrocardiography		○						
Lesion measurements* ²		○			○	○	○	○
Clinical assessments	Hematology* ³	○	○	○	○	○	○	○
	Blood biochemistry* ⁴	○	○	○	○	○	○	○
	Coagulation* ⁵	○	○	○	○	○	○	○
	Tumor markers* ⁶	○			○	○	○	
	Hepatitis virus	○						
Adherence to study treatment			○	○	○	○	○	
CRFs	Enrollment Eligibility Form	○						
	Patient Characteristics Report	○						
	Progress Report					○		
	Antitumor Effect Report					○	(○)	
	Treatment Completion Report						○	
	Treatment Suspension (Considering Discontinuation) Report						○	
	Follow-up Form							○

*1 Patient characteristics: Sex, height, pathological diagnosis, treatment history, disease stage, ECOG-PS, allergies, concomitant diseases

*2 Imaging: Lesions will be imaged by dynamic CT or dynamic MRI 4 weeks (± 1 week) after the start of treatment and every 8 weeks thereafter until progression is confirmed.

*3 Hematology parameters: Hemoglobin, white blood cell count, neutrophil count, red blood cell count, platelet count

*4 Blood biochemistry: AST, ALT, total bilirubin, direct bilirubin, ALP, γ -GTP, albumin, creatinine,

Na, K, Cl, amylase, lipase, blood glucose

*5 Coagulation profile: PT (INR)

*6 Tumor markers: AFP, AFP-L3 fraction, PIVKA-II

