11.6.2. Secondary endpoints

Progression-free survival (PFS)

The length of time from the date of randomization until diagnosis of recurrence or death from any cause, whichever is sooner.

Time to progression (TTP)

The length of time from the date of randomization until diagnosis of progression (PD) by the modified RECIST criteria. The date on which the investigator evaluates a patient and performs tests will be considered the date of progression as assessed by imaging. In the case of clinical progression, the date of the examination in which clear evidence of disease progression was observed will be considered the date of progression. Investigators will record the date progression was diagnosed and the reason on medical records. Patients whose disease does not progress as of the final follow-up point will be censored by the later of the last examination date and the last imaging test date for analysis. Patients who die before disease progression will be censored if the death was clearly unrelated to hepatocellular carcinoma or was due to rupture of gastroesophageal varices.

Overall response rate (ORR):

Will be determined using the modified RECIST criteria. Assessments will be made based on changes in the diameter of surviving tumors deemed viable by a modality such as contrast CT that are observed until completion or discontinuation of the protocol treatment.

Tumor markers:

Associations of baseline tumor marker levels and changes from baseline with efficacy will be explored.

Safety:

The Japanese translation of CTCAE v4.0 will be used to tabulate data for the safety population. The incidence and causality of each adverse event and serious adverse event will be tabulated by group and by CTCAE v4.0 grade. Blood pressure and other safety parameters will also be tabulated descriptively.

OS by tumor markers

Overall survival will be compared by tumor marker levels (AFP, AFP-L3, and PIVKA-II).

OS by Vp

Overall survival will be compared by Vp stage.

OS by response

OS will be compared between responders and non-responders

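### Two imaging schedules conflict and neither runs from randomisation, so TTP and PFS can be biased if scan timing differs by arm

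*Protocol*

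**What the plan says.** All references are to the protocol.

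- **Section 8.5** images lesions by dynamic CT or MRI 4 weeks (±1 week) "after the start of treatment and every 8 weeks thereafter until progression is confirmed". Footnote *2 of Table 11 (Section 8.6) repeats this.
- **Section 8.2.2** says "Data on the following parameters will be collected right before each cycle from the second cycle onward", and item 3 of its list is target lesion measurement. In Table 11 the lesion row is also marked in the column headed "Right before the start of each cycle". Section 6.1.1 states "This 4-week period constitutes one cycle", and Section 6.1.2 gives the same length for monotherapy, so this schedule is nominally 4-weekly.
- **Section 6.3.1**, headed as applying to both groups, lets cycles slip: "The start date of the next cycle can be extended for up to 8 weeks from the end of the previous cycle".
- **Sections 6.1.1 and 6.1.2** allow the first cycle to start up to 28 days after randomisation in either arm. Only 6.1.1 has reservoir placement, with sorafenib-free days around it, and only 6.1.1 allows sorafenib before the infusions.
- **Section 11.6.2** defines TTP as "The length of time from the date of randomization until diagnosis of progression (PD) by the modified RECIST criteria". PFS has the same origin.
- **Section 8.4** leaves tests after discontinuation to the investigator, "and will not be defined as part of this study", while its footnote says that patients without progression are followed until progression.

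**The concern.** A site cannot tell from the protocol whether a patient without progression should be scanned every 4 or every 8 weeks.

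A progression date can be no earlier than the scan that shows it. When the endpoint clock starts at randomisation and the scan clock starts at treatment or at each cycle, any systematic difference between arms in start date, cycle length or interval enters the TTP and PFS comparison as if it were a treatment difference.

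Nothing else in the protocol repairs this. The trial is open-label, and under Section 11.6.2 the investigator's assessment sets the progression date. Central review under Section 11.2 reads only the images from enrolment and from discontinuation or completion, so it cannot recover scans that were never taken in between. Patients who leave treatment without progression, for example because infusion becomes technically infeasible (Section 6.2), pass to follow-up with no stated imaging interval. At stake are two secondary endpoints, not OS.

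**Working it through.** **Step 1. The two calendars, in weeks from treatment start to week 52, cycles on time.**

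- Section 8.5: 4, 12, 20, 28, 36, 44, 52 = 7 scans.
- Section 8.2.2: 4, 8, 12, …, 52 = 52/4 = 13 scans.

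They agree at week 4. After that the intervals differ two-fold.

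**Step 2. Inputs for the size.** The protocol states no figure to reproduce here. Median TTP of 5.4 months for sorafenib monotherapy comes from Section 2.4.3: 5.4 × 30.4375/7 = 23.48 weeks. The exponential rate is λ = ln 2/23.48 = 0.02952 per week, with mean 33.87 weeks. There are 95 patients per arm (Section 0.6). Start lags and cycle delays by arm are not given, so those below are assumptions.

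**Step 3. Mean detection time.** With the first scan at week *a* after randomisation and interval *s*, the mean recorded time is a + s·exp(−λa)/(1 − exp(−λs)).

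- Lag 1 week, 8-weekly (a = 5): 5 + 8 × 0.8628/0.2103 = 37.81 weeks.
- Lag 3 weeks, 8-weekly (a = 7): 7 + 8 × 0.8133/0.2103 = 37.93 weeks. Difference 0.12 week.
- Same lag of 2 weeks (a = 6), 4-weekly: 6 + 4 × 0.8377/0.1114 = 36.09 weeks. The same lag, 8-weekly: 6 + 8 × 0.8377/0.2103 = 37.86 weeks. Difference about 1.8 weeks.

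A lag alone, under a common interval, hardly moves the mean. Different intervals by arm do.

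**Step 4. Effect on the log-rank comparison.** The simulation used identical true exponential TTP in both arms and dated progression at the next scan. Follow-up was cut at 78 weeks, with a one-sided 5% log-rank test, a one-step log-rank hazard ratio (combination versus monotherapy) and 500 trials per row. The Monte Carlo error is about 1 percentage point at 5%.

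| Scans | Lag, monotherapy / combination (weeks) | HR | Rejection for combination |
|---|---|---|---|
| 8-weekly both | 0–4 / 0–4 | 1.00 | 4.2% |
| 8-weekly both | 0–1 / 1–2 | 0.93 | 14.6% |
| 8-weekly both | 0–1 / 2–3 | 0.92 | 12.6% |
| 8-weekly both | 0–1 / 3–4 | 0.96 | 10.0% |
| 8-weekly both, reversed | 3–4 / 0–1 | 1.05 | 2.2% |
| 4-weekly both | 0–4 / 0–4 | 1.00 | 5.6% |
| 4-weekly both | 0–1 / 3–4 | 1.01 | 5.2% |
| 4-weekly, combination cycles 0–2 weeks late | 0–1 / 0–1 | 0.99 | 5.6% |
| 4-weekly, combination cycles 0–2 weeks late | 0–1 / 3–4 | 0.98 | 7.4% |
| 4-weekly, both arms' cycles 0–2 weeks late | 0–4 / 0–4 | 1.00 | 4.6% |
| Monotherapy 4-weekly, combination 8-weekly | 0–4 / 0–4 | 0.94 | 9.8% |

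Swapping the arms inverts the ratio, so reversed lags give about 1/0.956 = 1.05 to 1/0.918 = 1.09.

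The hazard ratio moves although the mean does not. At each monotherapy scan, the progressions of the past 8 weeks are all booked at once, against a risk set in which combination patients who have progressed but not yet been scanned still count as progression-free.

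The 4-weekly row with a 3–4 week lag is the only start lag run alone at that interval. It nearly realigns the two grids, so intermediate lags may leave somewhat more bias.

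**The case against.** The strongest case against is that no difference between arms is shown. The 28-day start window is the same in both arms and so is the 8-week limit on cycle delay. Once treatment starts, the Section 8.5 calendar is fixed and cycle delay cannot move it. Under Section 6.3.3, infusion toxicity in mid-cycle skips that cycle's infusions while sorafenib continues, and the next cycle depends on criteria common to both arms. If early sorafenib counts as the start of treatment, combination scans need not be late at all. All of this stands.

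A reader might therefore infer too much by concluding that progression *is* detected later in the combination arm. The documents do not support that: they give no lag or delay by arm, and the sign depends on both.

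A reader might also compare observed medians. With a true median of 23.48 weeks, scans at 5, 13, 21, 29 put the observed median at week 29 (6.7 months), and scans at 7, 15, 23, 31 put it at week 31 (7.1 months). That gap is an artefact of the scan grid. One more week of lag gives scans at 8, 16, 24 and an observed median at week 24 (5.5 months), while the mean shift in the first comparison is 0.12 week. Medians should not be used to size this.

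Two further replies have partial force. Footnote *2 can be read as qualifying the marks in the Table 11 lesion row, but Section 8.2.2 carries no such qualifier. After discontinuation, Section 8.3 asks for lesion measurement within 1 month, Table 11 marks lesion measurement, and the 8.4 footnote requires follow-up to progression. What is left open is the interval.

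**Conclusion.** The point holds as a contradiction plus a conditional risk of bias. The conflict between 8.2.2 and 8.5, the mismatch with the randomisation origin, and the gap between 8.4 and 8.5 are plain in the text.

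The bias arises only if start lags, cycle delays or the interval used differ by arm. It would most plausibly favour the combination, because reservoir placement and infusion toxicity exist only there, but this is a judgement and early sorafenib could reverse it. Under the assumed lags and no true effect, the apparent TTP hazard ratio is about 0.92–0.96 with 8-weekly scans, with a false-positive rate of two to three times the nominal 5%. It was negligible in the 4-weekly run with a start lag alone. Mean detection shifts by a fraction of a week under a common interval, and by about 1.8 weeks if the arms are scanned at different intervals.

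The simulation covers progression only. PFS also counts deaths, which are dated independently of scans, so the effect there should be smaller. OS does not depend on scans. The change is worth making for the secondary endpoints but does not threaten the primary conclusion.

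**What to change.** Reconcile Sections 8.2.2 and 8.5 and Table 11 to a single efficacy-imaging interval. Count scan dates from randomisation, with the same window in both arms, regardless of treatment start, cycle delay or discontinuation, until progression. Have Section 8.4 refer to that schedule for patients who are off treatment without progression. Dating from randomisation also removes the ambiguity over what starts treatment when sorafenib precedes the infusions.

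With the same scan timing in both arms the simulated artefact disappears under either interval (HR 1.00; rejection 4.2% at 8 weeks, 5.6% at 4 weeks), so the choice between them can rest on other grounds.

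The cost is protocol wording, and some scans will no longer coincide with a cycle visit. For patients whose scans are already done the wording cannot help. There, tabulate actual scan dates from randomisation by arm and add an interval-censored sensitivity analysis of TTP and PFS.
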